10.1 Trial Interventions

Trial Arm 1. Intervention 1 – Self-directed CBT smartphone application *ClearlyMe*: Participants allocated to this condition will receive *ClearlyMe*. *ClearlyMe* is a free, self-directed CBT-based smartphone application that provides therapeutic content and symptom management strategies to adolescents experiencing mild to moderate depressive and anxiety symptoms. The application was specifically designed for adolescents by a multidisciplinary team of psychologists, researchers, user experience designers and software developers at the Black Dog Institute. *ClearlyMe* is delivered as an autonomous, non-sequential CBT program consisting of 37 brief lessons (i.e., therapeutic content alongside activities). Lessons include the following evidence-based treatment components: psychoeducation, cognitive restructuring, emotion awareness and acceptance, goal setting, problem solving, activity scheduling, behavioural activation, exposure, relaxation, mindfulness, and values labelling. The lessons also encourage participants to practise the psychological skills in-between lessons and return to the app to reflect or access further content as needed. The lessons vary in length, taking between 5 to 10 minutes each to complete. To help navigate the program content, users are encouraged to complete the lessons via nine curated ‘collections’. A collection is defined as a structured selection of related lessons grouped together with a brief title and introduction. Each collection varies in length, taking approximately 20 minutes to complete. Users can also complete the individual lessons from a ‘show all’ list whereby they self-select lessons considered to be relevant to their individual needs. In this list, lessons are categorised into three groups depending on their target: ‘emotions’, ‘thoughts’, ‘behaviours’. The app also includes a Moodcheck (i.e., brief mood monitoring), Mind Hacks (i.e., quick strategies that help in the moment), and Stories (i.e., short videos of young peoples’ experience managing mental health symptoms and positive help-seeking experience) to provide users with additional pathways to accessing therapeutic content. For these features, specific lessons are recommended after the feature is accessed. *ClearlyMe* also includes in-app reminders, ‘saving’ and ‘favourite’ functions to support users to return to the app to reengage in content. In-app reminders include a ‘revisit the app’ reminder, which notifies all participants to use the app if they haven’t done so in the past 7 days. This reminder is locked and cannot be turned off in the app. Users can also set an additional reminder to use the Moodcheck feature once a day for as many days as they wish. Due to the developer requirements of iOS app store and Google Play, app notifications must be able to be disabled in a user’s phone settings. The app also includes a ‘Get Help’ section that contains information of when and where to access additional mental health support services (e.g., Kid’s Helpline). Appendix E includes the full product information. To ensure compliance, participants who fail to download the *ClearlyMe* app within 7 days of randomisation will be sent an email and SMS reminder to download the app.

Participant instructions for use: In this trial, participants are provided with access to *ClearlyMe* for 6-weeks. Participants are instructed to complete the app content by undertaking at least one collection per week (approximately 20 minutes) for the intervention period; however, participants can complete the app content in any order and according to their preferences. Participants are also instructed to use the ‘Get Help’ section of the app if they feel they require extra mental health support during the intervention period, although this section of the app is not monitored in real-time by the research team. To further ensure compliance, all participants in this intervention arm will be sent one SMS per week from the Black Dog Institute Research Engine reminding them to use the *ClearlyMe* app. Participants allocated to this intervention arm will not receive any additional human

contact from the research team, unless technical support for the smartphone application (via email) is required.

Trial Arm 2. Intervention 2 – Guided use of CBT smartphone application *ClearlyMe*: Participants allocated to this condition will receive the same intervention provided in Trial Arm 1, with the addition of a weekly guided support session. This will take place in the form of a SMS chat provided by the research team for the duration of the intervention period. Participants will be contacted via SMS on their mobile phone number at the times provided to participants after randomisation (4pm to 7pm Monday to Friday). Contact will be made weekly, with one additional attempt made for non-response (two days apart, total of 2 contact attempts in 7 day period). In total, participants in this condition will receive 6 weekly support sessions in the intervention period. Personnel conducting the guided sessions will be research employees of the Black Dog Institute and will use a standard script, with a decision flow chart to direct the chat (see Appendix F). The SMS chat will consist primarily of technical support with some low intensity motivational coaching. Research Assistants (RAs) not clinicians, will be trained to conduct these sessions and will be supervised by a clinician. The clinician will be available during these sessions to support the RA if needed. The guided support sessions will be designed to be conducted in one sitting (i.e., within 20 minutes) but duration and script compliance will be recorded by the research assistants.

Participant instructions for use: In this trial, participants are provided with access to *ClearlyMe* for 6-weeks. Participants are instructed to complete the app content by undertaking at least one collection per week (approximately 20 minutes) for the intervention period; however, participants can complete the app content in any order and according to their preferences. Participants are also instructed to use the ‘Get Help’ section of the app if they feel they require extra mental health support during the intervention period, although this section of the app is not monitored in real-time by the research team. Participants will be instructed that they can expect a weekly SMS chat for the duration of the study period any time between the hours of 4pm to 7pm Monday to Friday.

Trial Arm 3. Active attention-matched control – SMS enabled, self-directed low intensity weekly psycho-education flyers with self-care:

This study will utilise an active attention matched control condition. Participants allocated to this condition will receive 6 weekly psychoeducation modules delivered via SMS with handouts that can be accessed on their mobile device. The psycho-education consists of 6 topics: What is mental health, Feeling on Edge – Understanding Anxiety, Waves of Sadness – Understanding Depression, When it’s time to tell someone, When a friend needs a hand, and When friendships are complicated. Each module consists of information about mental health problems, links to credible Australian mental health organisations, and finishes with selfcare suggestions for what a young person can do right now if they are feeling worried or down. These modules were developed by the Black Dog Institute, created by mental health professionals, researchers and young people. Each module takes approximately 20 minutes to complete. A full overview of the psychoeducation content is provided as in Appendix G. Participants allocated to this intervention arm will not receive any additional human contact from the research team, unless technical support for the program (via email) is required. At the primary endpoint, participants will receive one email that contains all of the psycho-education material in one collated document for future use.

Participant instructions for use: In this trial, participants are provided with access to the digital psychoeducation content for the 6-week intervention period. Participants will be instructed to complete the content by undertaking one module per week (approximately 20 minutes) for the intervention period. Participants are also instructed to use the ‘Get Help’ section of the study site if they feel they require extra mental health support during the intervention period, although this is not monitored by the research team.

11. Safety and Monitoring

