H1= Participants who receive *ClearlyMe* (both self-directed and guided use) will report greater reductions in depressive symptoms between baseline and primary endpoint as well as baseline and secondary endpoint when compared to participants in the control condition;

H2= Participants who receive *ClearlyMe* (both self-directed and guided use) will report greater improvements in secondary outcomes (anxiety, psychological distress, emotional wellbeing,

quality of life, rumination, emotion regulation and CBT skill acquisition) between baseline and primary endpoint as well as baseline and secondary endpoint when compared to participants in the control condition;

H3= Participants' engagement with and completion of *ClearlyMe* will be significantly higher among participants who receive guided support when compared to participants who receive self-directed use.

Other exploratory hypotheses:

H4= Improvements in depressive symptoms among users of *ClearlyMe* will be moderated by gender, age, history of mental health, symptom severity at baseline, greater perceived need for care and higher levels of openness to digital mental health.

H5= Improvements in depressive symptoms among users of *ClearlyMe* will be mediated by rumination, emotion regulation, CBT skill acquisition, digital therapeutic alliance, and rates of engagement/completion.

5. Background Information

Adolescence is a significant and sensitive stage of life, whereby individuals evolve physically, socially, and psychologically as they transition to adulthood (Dahl et al., 2018). Given the rapid changes in a young person's development, this period also presents important risks and opportunities for young people's mental well-being. For example, a young person's access to a supportive environment, ability to maintain healthy sleeping and exercise behaviours, learn and develop coping, problem solving, emotional and interpersonal skills can influence their mental health (WHO., 2020). Poor mental health can have detrimental consequences to a young person's quality of life and their ability to function socially and academically (McGorry et al., 2011; Patel et al., 2007). Recent research suggests the global prevalence of depressive and anxiety symptoms in children and adolescents during the COVID-19 pandemic has increased, with 1 in 4 experiencing elevated depressive symptoms and 1 in 5 experiencing elevated anxiety symptoms, highlighting the need for mental health care (Racine et al., 2021).

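### The control is attention-matched to self-directed ClearlyMe only, yet the label is unqualified and H1 also sets the guided arm against it

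*Protocol*

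**What the plan says.** Section 10.1, under Trial Arm 3, states: "This study will utilise an active attention matched control condition". The aims in section 4 and in Appendix I use the same description. None of the three places says which ClearlyMe arm the matching refers to.

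H1 in section 4 predicts that participants who receive ClearlyMe ("both self-directed and guided use) will report greater reductions in depressive symptoms between baseline and primary endpoint") will do better than those in the control condition. The sentence that introduces the hypotheses says the trial will determine whether the smartphone application is effective against guided use and the attention-matched control. Guided use is thus a comparator to ClearlyMe in that sentence and a form of ClearlyMe in H1.

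Section 10.1 schedules the arms as follows.

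- **Control:** "Each module takes approximately 20 minutes to complete", and "Participants will be instructed to complete the content by undertaking one module per week (approximately 20 minutes) for the intervention period". Participants get no "additional human contact from the research team, unless technical support for the program (via email) is required".
- **Self-directed:** participants are told to complete the content by "undertaking at least one collection per week (approximately 20 minutes) for the intervention period". In addition, "all participants in this intervention arm will be sent one SMS per week from the Black Dog Institute Research Engine". Human contact is again limited to technical support by email.
- **Guided:** the Arm 1 intervention with the same app instruction, plus six weekly SMS chats run by trained research assistants. The content is mainly technical support with some motivational coaching. On length: "The guided support sessions will be designed to be conducted in one sitting (i.e., within 20 minutes").

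**The concern.** An attention-matched control exists so that a difference from it cannot be put down to time spent or contact received. That protection covers self-directed versus control. It does not cover guided versus control, because nothing in the control schedule corresponds to the chats.

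The problem arises if guided use beats control and self-directed use does not. Under the lead-in sentence and H1 as written, that result would count as ClearlyMe being effective against an attention-matched control. Extra time and human contact could equally explain it. The protocol itself expects guidance to matter: section 8 plans a larger effect for guided than for self-directed CBT, H3 predicts higher engagement with guidance, and section 5 links human support to adherence.

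**Working it through.** **Scheduled exposure, from section 10.1**

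| | Control | Self-directed | Guided |
|---|---|---|---|
| Instructed content per week | about 20 min | at least about 20 min | at least about 20 min |
| Scheduled chat per week | 0 | 0 | up to 20 min |
| Total per week | about 20 min | about 20 min | 20 + 20 = up to about 40 min |
| Over 6 weeks | 6 × 20 = 120 min | 6 × 20 = 120 min | 6 × 40 = up to 240 min |
| Scheduled human sessions | 0 | 0 | 6 |

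Totals take the instructed minimum of one collection a week in the app arms. On that basis, self-directed to control is 120/120 = 1.0 with 0 against 0 human sessions. Guided to control is up to 240/120 = 2.0 with 6 against 0.

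**Planning values, from section 8:** psychoeducation 0.10, self-directed 0.35, guided 0.65.

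- Guided minus control: 0.65 − 0.10 = 0.55.
- Self-directed minus control: 0.35 − 0.10 = 0.25.
- Guided minus self-directed: 0.65 − 0.35 = 0.30.

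**How plausible is a guided-only result?** The planned sample size reproduces. A two-sided t-test at 0.05 with power 0.80 and d = 0.35 needs 130 per arm; 130/0.80 = 162.5, so 163 per arm; 3 × 163 = 489. Completers are then 163 × 0.80 = about 130 per arm.

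- *If the section 8 values are effects within each arm*, so that differences between arms are 0.25 and 0.55: power is 0.52 for self-directed versus control and 0.99 for guided versus control. The probability that guided is significant and self-directed is not lies between 0.99 − 0.52 = 0.47 and 1 − 0.52 = 0.48.
- *If 0.35 is already a difference from control*, which is the only reading that returns 489: power for self-directed versus control is 0.80, and the probability of a guided-only result is at most 1 − 0.80 = 0.20.

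Section 8 does not say which reading is meant. Under either, a guided-only result is a realistic outcome. The adequacy of 489 is a separate matter, and the point here does not rest on it.

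**The case against.** The case on the other side has substance, and much of it stands.

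- A reader might infer that the protocol claims a match to both ClearlyMe arms. It never says so. The control's content and delivery closely mirror Arm 1, and matching to self-directed use is a fair reading. The defect is an unqualified label on the only control, combined with an H1 that tests both arms against it.
- H1 names guided use openly, and section 10.1 defines Arm 2 as the app with support added. Guided versus control is a sound randomised comparison of that package, and nothing here makes it invalid.
- The three arms can separate the effects when results are reported by arm. The protocol does not say that the app arms will be pooled, or that a guided-only win will be reported as efficacy of the app.
- The 40 and 240 minutes are ceilings, because 20 minutes is the design length of a chat. The 12 SMS per week in section 10 (12 × 6 = 72 over the trial) is a reimbursement estimate and should not be read as a contact schedule.
- It is tempting to divide the planning values and say that 0.30/0.55 = 55% of the guided contrast is guidance and 45% is the app, or that reading it as the app effect overstates that effect 0.55/0.25 = 2.2-fold. The documents do not support this. Section 5 links human support to adherence, H3 expects more engagement with guidance, and H5 lists engagement as a mediator. Part of the 0.30 may therefore be the app working through greater use.

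What survives is that the label and the lead-in to H1 are protocol text, fixed before any analysis, and they allow a conclusion that the guided contrast cannot carry.

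**Conclusion.** The point holds in limited form. The attention-matched property is true of self-directed versus control, on instructed time and scheduled human contact. It is not true of guided versus control, where the difference is up to about 20 minutes a week and six human sessions. Guided versus control therefore estimates the effect of ClearlyMe plus weekly human support, and cannot alone show that the app works beyond attention.

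On the planning values, the total increment from adding guidance is 0.30, with no split between app and non-app routes implied. This rests on scheduled rather than actual exposure. Section 10.1 has chat duration recorded, and section 10 has app usage collected, so actual exposure in the app arms can be described later. The defect lies in wording and interpretation; arms, randomisation and contrasts are sound.

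**What to change.** 1. In the section 4 aims and hypothesis lead-in, the Trial Arm 3 description in section 10.1, and the Appendix I aims, limit the attention-matched description to self-directed versus control.
2. State H1 by arm: (a) self-directed versus control addresses whether ClearlyMe works beyond attention; (b) guided versus control is the effect of ClearlyMe plus weekly human support, and is not attention-matched.
3. State that a positive result for the guided arm alone will not be reported as effectiveness of the app alone.
4. Report guided versus self-directed on the PHQ-A as the guidance increment. The section 4 aim already names this comparison, but H3 covers only engagement and completion. At the planned 0.30 with 130 completers per arm, power is about 0.67, so present it as an estimate with its interval.

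The cost is a wording amendment, with ethics committee approval if it is treated as a deviation from the statistical plan under Appendix J. Arms, schedule, data and sample size do not change. The downside is a narrower claim for the guided arm.

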11.1 Assessment of Safety Event Report Forms

Safety reports will be assessed on the seriousness, causality, and expectedness of the event to the trial treatment(s), intervention(s), investigational medical product(s), investigational medical device(s). The following are known and expected adverse effects, harms, risks or discomforts associated with trial procedures, treatments or interventions.

a) Known Adverse Effects

Effect/Event	Criteria
Frequent, current suicidal ideation (i.e., thoughts of death or of harming oneself) detected through the self-report Patient Health Questionnaire-9, at baseline, primary or secondary endpoint.	A participant reports an item score of ≥ 2 (“More than half the days” to “Nearly every day”) on item 9 of the PHQ-9 (i.e., “Over the last two weeks, how often have you had thoughts that you would be better off dead, or of hurting yourself in some way?”)
Action	

The following actions will occur when a participant satisfies the above criteria:
 
a) A pop-up message in the questionnaire will be displayed on participants’ device. This message will provide individuals with immediate recognition of their response and recommend they tell someone they trust about how they are currently feeling. This message will read: “Your responses have indicated that you may not be doing so well right now. Thanks for letting us know. We think it’d be great if you could tell a trusted adult about how you’re feeling. If you’re not up to talking to someone you know, try Kids Helpline on [name] or Lifeline [name]. We also recommend you check out the Get Help section in the top right corner of this site” .
 
b) These participants will also be invited to request a call back from the research team’s clinical psychologist. The following message will be displayed on the participant’s screen: “Would you like to receive a confidential call from a psychologist from the research team?” with the option to choose ‘yes’ or ‘no’. If the participant selects ‘yes’ for a call back, the Black Dog Institute Research Engine will generate an email notification to the Trial Manager that contains the participant’s study ID code, first name, mobile number, and preferred call time. The Trial Manager will arrange for the Clinical Psychologist to attempt contact with the participant within two working days. The Clinical Psychologist will conduct a brief risk assessment over the phone to determine the level of suicide risk. If determined to be at risk, the participant will be advised to contact an appropriate service (e.g., a GP, the BDI Psychology Clinic, Mental Health Hotline). If the risk of harm is deemed significant enough to break confidentiality, or the participant requests it, their parents will be contacted by mobile telephone within an additional two working days. Referral suggestions will be provided. [name], the
	


Trial Manager and the research team’s qualified clinical psychologist has significant experience in working with distressed youth both in research and clinical settings. [name] is well equipped to oversee and manage any issues that may arise. All participants who receive a call back will be offered an additional follow-up call, scheduled 7 days after the initial call, to check-in about the agreed safety plan. In all instances, if a participant is unable to be contacted by phone after two attempts, they will be sent an email from the study email address informing them of the attempt to make contact. This email will also contain mental health information and support services.
 
c) A register of these events and associated interactions (i.e., telephone call attempts, times, dates, outcomes) will be recorded in a separate risk management spreadsheet managed by the Trial Manager. These events will also be recorded in the UNSW Safety Monitoring Template.
	
Effect/Event	Criteria

Severe depressive symptoms detected at final study assessment (i.e., secondary endpoint: 4-months post-baseline) through the self-report Patient Health Questionnaire-9.
	
A participant reports a total score ≥ 20 on the Patient Health Questionnaire-9 at secondary endpoint assessment (i.e., 4-months post-baseline).

Action	

The following actions will occur when a participant satisfies the above criteria:
 
a) A pop-up message in the questionnaire will be displayed on participants’ device. This message will provide individuals with immediate recognition of their response and recommend they tell someone they trust about how they are currently feeling. This message will read: “Your responses have indicated that you may not be doing so well right now. Thanks for letting us know. We think it’d be great if you could tell a trusted adult about how you’re feeling. If you’re not up to talking to someone you know, try Kids Helpline on [name] or Lifeline [name]. We also recommend you check out the Get Help section in the top right corner of this site.”
 
b) These participants will also be invited to request a call back from the research team’s clinical psychologist. The following message will be displayed on the participant’s screen: “Because you are coming to the end of the study, we’d like to offer you the opportunity to talk to a mental health professional from the Black Dog Institute about how you have been feeling lately. Would you like to receive a confidential call from a psychologist from the research team?” with the option to choose ‘yes’ or ‘no’. If a participant selects ‘yes’, the Black Dog Institute Research Engine will generate an email notification to the Trial Manager that contains the participant’s study ID code, first name, mobile number, and preferred call time. The Trial Manager will arrange for the Clinical Psychologist to attempt contact with the participant within two working days. The Clinical Psychologist will conduct a brief risk assessment over the phone to determine the level of depressive symptoms and if necessary, the presence of suicidality. If determined to be at risk, the participant will be advised to contact an appropriate service (e.g., a GP, the BDI Psychology Clinic, Mental Health Hotline). If the risk of harm is deemed significant enough to break confidentiality, or the participant requests it, their parents will be contacted by mobile telephone within an additional two working days. Referral suggestions will be provided. [name], the Trial Manager and the research team’s qualified clinical psychologist has significant experience in working with distressed youth both in research and clinical settings. [name] is well equipped to oversee and manage any issues that may arise. All participants who receive a call back will be offered an additional follow-up call, scheduled 7 days after the initial call, to check-in about the agreed safety plan. In all instances, if a participant
	


is unable to be contacted by phone after two attempts, they will be sent an email from the study email address informing them of the attempt to make contact. This email will also contain mental health information and support services.
 
c) A register of these events and associated interactions (i.e., telephone call attempts, times, dates, outcomes) will be recorded in a separate risk management spreadsheet managed by the Trial Manager. These events will also be recorded in the UNSW Safety Monitoring Template.
	
Effect/Event	Criteria

Mental health related hospitalisation reported at primary or secondary endpoint or disclosed in any other study procedures (e.g. call back phone calls, participant emails).
	
Participants reports yes to the item “Throughout the study, have you had any mental health problems where you had to go to a hospital emergency department, or had to stay in hospital for more than one day?” in the primary and secondary endpoint study assessments, or, reports this event via other study procedures and activities.

Action	

All relevant study data for this event will be recorded in the UNSW Safety Monitoring Template for reporting.
	
Effect/Event	Criteria

Self-identified deterioration in mental health due to study activities reported by participants at primary or secondary endpoints.
	
Participants reports yes to the item “At any point throughout the study, did you feel that any of the study activities made your mental health or feelings of depression, anxiety or suicidality worse?” in the primary and secondary endpoint assessments, or, reports this event via other study procedures and activities.

Action	

All relevant study data for this event will be recorded in the UNSW Safety Monitoring Template for reporting.
	

b) Known Harms, Risks or Discomforts

The interventions evaluated in this trial have been designed and reviewed by mental health professionals to support young people to manage their mental health. The researchers do not anticipate significant harm or distress related to use of the interventions in the current trial, however, the following harms, risks or discomforts may occur:

- a) While CBT is the gold-standard treatment for depression and anxiety, CBT-based activities undertaken in the trial interventions may require emotional effort to complete and have the potential to cause a transient increase in depressive and anxiety symptoms as well as psychological distress (e.g., exposure therapy and behavioural experiments).

- b) While completion of self-report questionnaires about one's mental health have not been shown to increase distress, some participants may experience some emotional discomfort related to being asked about their mental health during the study assessments.

To minimise the potential known harms, risks or discomforts, various safety procedures will be implemented throughout the trial:

- All participants not meeting inclusion criteria at screening, including those deemed ineligible because of severe depressive symptoms and significant suicidality, will be provided with a list of referral services and information on how to access mental health crisis services. This information is provided in Appendix A.
- To mitigate potential discomfort or distress associated with the study assessments, brief youth-friendly versions have been used where possible.
- At the beginning of the study, participants will be advised that the trial interventions are not intended to replace professional medical advice, or to provide crisis support. Participants are also able to seek unlimited mental health treatment and support throughout the study period.
- A list of mental health support services will be provided to participants when completing the study assessments via the "Get Help Now" section of the study assessment websites. This list will also be shown to participants upon completion of each study assessment (see Appendix D).
- Information regarding how participants can contact the research team, how often the trial email is checked, and response time will also be provided in the study welcome email.
- All trial interventions contain emergency help information that can be accessed at any time during the intervention period.
- In addition to external support resources, participants will be informed in the PICF that they can contact the research team if they become upset or distressed because of their participation in the study. If a young person contacts the research team, a psychologist from the research team will arrange follow-up contact to assess the level of distress and direct the young person to the appropriate services. This will be provided free of charge.

How benefits outweigh potential risks of discomfort/harms:

- CBT is the gold-standard, first line treatment for depressive and anxiety symptoms in adolescents. Psychoeducation is also an evidence-based approach to reducing depressive symptoms. Therefore, all participants in the current trial will receive access to trusted mental health information and activities developed by a reputable Australian mental health organisation (The Black Dog Institute). We expect therefore, that the benefits of interventions outweigh any potential risks of discomfort or harm associated with completing the study activities.
- The interventions in this study may also lead to increased help-seeking and greater engagement with other mental health services and support among participants.
- Participants' involvement in the trial and engagement with the program has the potential to increase their mental health literacy and self-awareness, which is important to maintain psychological wellbeing across the lifespan.

